#### **6.9.2 Specific toxicity management and dose modification information - sorafenib**

**CCI mg CCI**

Investigators should follow local standard clinical practice regarding dose modifications for agents used in the sorafenib **CCI mg CCI** arm. For specific information regarding the individual agent used in this study, please refer to the local prescribing information for the relevant agent.

#### **6.9.3 Management of Hepatotoxicity**

Management of hepatotoxicity should take into consideration the viral status of the patient as well as the type of toxicity observed. In general, while both ALT and AST will be monitored, ALT is considered to be more liver specific; therefore, changes in ALT should be the primary driver for dose modification and management decisions. In addition, isolated increases in ALT without other signs of hepatotoxicity (such as fever, hyperbilirubinemia, and worsening ascites), which have been observed in patients treated with tremelimumab monotherapy (Sangro et al 2013), should be considered to be of a different risk-benefit profile from increases in ALT associated with other signs of hepatotoxicity.

General guiding principles for select patient populations are as follows:

1. Uninfected HCC: Interpretation of hepatic laboratory results not confounded by underlying viral infection. Management should focus on ruling out non-imAEs and early intervention with steroids and/or other immunosuppressive agents as clinically appropriate
2. HCV+ or HBV+ HCC: Differential diagnosis for isolated increases in ALT could include the following:
  - a. Activation of the immune system resulting in increased immune response to HCV or HBV manifesting as decreases in viral replication, decreases in HCV viral load, or decreases in HBsAg
  - b. Changes in immune response to HCV or HBV leading to increased HCV or HBV viral replication, increases in HCV viral load, or increases in HBV viral load/HBsAg (primarily a hypothetical risk given the mechanism of action of durvalumab and tremelimumab)
  - c. Non-imAEs unrelated to HCV or HBV
  - d. imAEs such as autoimmune hepatitis

Increases in ALT attributable to changes in HCV status do not necessarily require immediate immunosuppression. Rather, only in the setting of imAEs would immunosuppression (eg, corticosteroids) be considered. Antiviral therapy may be considered in the setting of an ALT increase due to increased HCV viral replication.

Increases in ALT attributable to changes in HBV viral replication do not necessarily require immediate intervention and/or immunosuppression, with the exception of increases in HBV viral load. Increases in HBV viral load suggest onset of resistance to anti-HBV therapy, which should precipitate a change in anti-HBV therapy. Only in the setting of imAEs would immunosuppression (eg, corticosteroids) be considered.

Liver biopsy is recommended soon after the AE is reported as a way to understand the underlying pathology and determine the best type of intervention. Suggested laboratory tests to monitor liver status include AST, ALT, TBL, direct bilirubin, albumin, alkaline phosphatase (ALP), gamma glutamyltransferase, and INR. Patients should be monitored/evaluated for etiologies (eg, viral hepatitis, disease progression, concomitant medications, herbals, over-the-counter medications, and supplements) other than immune-related hepatotoxicity before the initiation of dose modifications and immunosuppression.

Treatment modification and management guidelines for hepatotoxicity are presented in the Toxicity Management Guidelines.

## **6.10 Study governance and oversight**

### **6.10.1 Data Monitoring Committee**

An IDMC will be established to monitor data on an ongoing basis to ensure the continuing safety of patients enrolled in this study, to ensure the integrity of the study, and to oversee the 2 planned interim analyses. The first IDMC safety review will occur when approximately

30 patients per arm are randomized or 6 months after the first patient is dosed (whichever occurs first) and will occur approximately every 6 months thereafter; the frequency of IDMC review may be adjusted by the IDMC as needed. The IDMC will be composed of individuals external to AstraZeneca. An IDMC charter will be developed which will specify the Committee's responsibilities, authorities, and procedures along with details of the interim analysis planning, decision-making guidance, and dissemination of the results as well as the recommendations and decisions after the interim analyses. Formal implementation and communication of IDMC recommendations will be managed by the AstraZeneca Executive Committee, which will be unrelated to the study project team.

Full details of the IDMC procedures, processes, and interim analyses can be found in the IDMC Charter.

## 7. STUDY DRUGS AND OTHER TREATMENTS

## 7.1 Identity of study drugs

AstraZeneca will supply durvalumab and tremelimumab. Sorafenib will be supplied locally. Additional details are provided below.

Investigational product	Dosage form and strength
Durvalumab	CCI mg/mL solution for infusion after dilution
Tremelimumab	CCI mg/mL solution for infusion after dilution
Sorafenib a	CCI mg CCI -mg tablets) orally CCI

**BID** twice daily.

a Under certain circumstances when local sourcing is not feasible, sorafenib treatment may be supplied centrally through AstraZeneca.

### 7.1.1 Durvalumab

Durvalumab will be supplied by AstraZeneca as a **CCI** mg vial solution for infusion after dilution. The solution contains **CCI**

Investigational product vials are stored at 2°C to 8°C (36°F to 46°F) and must not be frozen. Drug product should be kept in secondary packaging until use to prevent excessive light exposure.

## Preparation of durvalumab doses for administration with an IV bag

The dose of durvalumab for administration must be prepared by the Investigator's or site's designated IP manager using aseptic technique. Total time from needle puncture of the durvalumab vial to the start of administration should not exceed the following:

- 24 hours at 2°C to 8°C (36°F to 46°F)
- 4 hours at room temperature

The infusion solution must be allowed to equilibrate to room temperature prior to administration.

A dose of **CCI** (for patients weighing >30 kg) will be administered using an IV bag containing **CCI** (w/v) saline or **CCI** (w/v) dextrose, with a final durvalumab concentration ranging from **CCI** to **CCI** mg/mL, and will be delivered through an IV administration set with a **CCI** or **CCI**  $\mu$ m filter. **CCI** milligrams of durvalumab (ie, 30.0 mL of durvalumab) will be added to the IV bag. The IV bag size should be selected such that the final concentration is between **CCI** to **CCI** mg/mL. The bag will be mixed by gently inverting to ensure homogeneity of the dose in the bag.

If the patient's weight falls to  $\leq$ 30 kg, weight-based dosing at **CCI** mg/kg will be administered using an IV bag containing **CCI** (w/v) saline or **CCI** (w/v) dextrose, with a final durvalumab concentration ranging from **CCI** to **CCI** mg/mL, and will be delivered through an IV administration set with a **CCI** or **CCI**  $\mu$ m filter. [Appendix F](#) includes an example of a weight-based dose calculation.

The standard infusion time is 1 hour ( $\pm 5$  minutes). In the event that there are interruptions during infusion, the total allowed infusion time should not exceed 8 hours at room temperature. Other drugs should not be co-administered through the same infusion line.

The IV line will be flushed with a volume of IV diluent equal to the priming volume of the infusion set used after the contents of the IV bag are fully administered, or the infusion will be completed according to institutional policy to ensure the full dose is administered. It will be documented if the line was not flushed.

If either preparation time or infusion time exceeds the time limits a new dose must be prepared from new vials. CCI [REDACTED], and any unused portion must be discarded.

Preparations are to be carried out in accordance with the study-specific drug handling instructions.

#### 7.1.2 Tremelimumab

Tremelimumab will be supplied by AstraZeneca as a CCI mg or CCI mg vial solution for infusion after dilution. The solution contains CCI [REDACTED]

[REDACTED] and a density of 1.034 g/mL. The nominal fill volume is CCI mL for the CCI mg vial and CCI mL for the CCI mg vial.

Investigational product vials are stored at 2°C to 8°C (36°F to 46°F) and must not be frozen. Drug product should be kept in secondary packaging until use to prevent excessive light exposure.

#### Preparation of tremelimumab doses for administration with an IV bag

The dose of tremelimumab for administration must be prepared by the Investigator's or site's designated IP manager using aseptic technique. Total time from needle puncture of the tremelimumab vial to the start of administration should not exceed the following:

- 24 hours at 2°C to 8°C (36°F to 46°F)
- 4 hours at room temperature

The infusion solution must be allowed to equilibrate to room temperature prior to administration.

A dose of CCI mg or CCI mg (for participants >30 kg in weight) will be administered using an IV bag containing CCI [REDACTED] with a final tremelimumab concentration ranging from CCI to CCI mg/mL and delivered through an IV administration set with a CCI or CCI- $\mu$ m filter. Add CCI mL (i.e. CCI mg; dose volume rounded to nearest tenth

mL) or **CCI** (i.e. **CCI** mg) of tremelimumab to the IV bag. The IV bag size should be selected such that the final concentration is within **CCI** to **CCI** mg/mL. Mix the bag by gently inverting to ensure homogeneity of the dose in the bag.

If the patient's weight falls to  $\leq 30$  kg, weight-based dosing of either 1 (for **CCI** mg **CCI** group) or **CCI** mg/kg (for **CCI** mg **CCI** group) will be administered using an IV bag containing **CCI** (w/v) saline or **CCI** (w/v) dextrose, with a final tremelimumab concentration ranging from **CCI** to **CCI** mg/mL, and will be delivered through an IV administration set with a **CCI** or **CCI**- $\mu$ m filter.

[Appendix G](#) includes an example of a weight-based dose calculation. The standard infusion time is 1 hour ( $\pm 5$  minutes). Less than 55 minutes is considered a deviation. In the event that there are interruptions during infusion, the total allowed infusion time should not exceed 8 hours at room temperature. Other drugs should not be co-administered through the same infusion line.

The IV line will be flushed with a volume of IV diluent equal to the priming volume of the infusion set used after the contents of the IV bag are fully administered, or the infusion will be completed according to institutional policy to ensure the full dose is administered. It will be documented if the line was not flushed.

If either preparation time or infusion time exceeds the time limits, a new dose must be prepared from new vials. Tremelimumab does not contain preservatives, and any unused portion must be discarded. Preparations are to be in accordance with the study-specific drug handling instructions.

### 7.1.3 Sorafenib

Sorafenib will either be locally sourced or centrally supplied by AstraZeneca and will be administered according to prescribing information or treatment guidance in general use by the investigating site. Under certain circumstances when local sourcing is not feasible, AstraZeneca will centrally supply the drug, and the drug will be labeled with text translated into local language in accordance with regulatory guidelines.

## 7.2 Dose and treatment regimens

Patients will be randomized in a 1:1:1:1 ratio to 1 of 4 treatment arms:

- Arm A: durvalumab **CCI** mg monotherapy,
- Arm B: durvalumab **CCI** mg plus tremelimumab **CCI** mg **CCI** combination therapy,
- Arm C: durvalumab **CCI** mg plus tremelimumab **CCI** mg **CCI** combination therapy, or

- Arm D: sorafenib **CCI** mg **CCI**

[figure not shown]
Crossover within the study will not be permitted for any of the treatment arms, except for rechallenge in Arm B. Following amendment 4 patients will be randomized in a 1:1:1 ratio to 1 of 3 treatment arms: Arm A, Arm C and Arm D.

### **Durvalumab monotherapy (Arm A)**

Patients in Arm A will receive **CCI** mg durvalumab via IV infusion **CCI** starting on **CCI** until confirmed PD, unacceptable toxicity, or any discontinuation criterion are met (Figure 2). (Note: If a patient's weight decreases to  $\leq 30$  kg, the patient should receive weight-based dosing of durvalumab **CCI** mg/kg **CCI** after consultation between the Investigator and the Study physician, until the weight increases to  $>30$  kg, at which point the patient should receive the fixed dose of durvalumab **CCI** mg **CCI**.)

Standard infusion time is 1 hour ( $\pm 5$  minutes). Less than 55 minutes is considered a deviation. In the event that there are interruptions during infusion, the total allowed time should not exceed 8 hours at room temperature.

**Figure 2** **Durvalumab monotherapy dosing schedule**

Durva Durvalumab; D/C Discontinuation; PD Progressive disease.

[figure not shown]
### **Durvalumab **CCI** mg plus tremelimumab **CCI** mg **CCI** combination therapy (Arm B)**

Patients in Arm B will receive durvalumab **CCI** mg plus tremelimumab **CCI** mg **CCI** starting at **CCI** followed by durvalumab **CCI** mg monotherapy **CCI** starting **CCI** after the final infusion of the combination therapy until confirmed PD, unacceptable toxicity, or any discontinuation criteria are met (Figure 3). (Note: If a patient's weight decreases to 30 kg or below ( $\leq 30$  kg), the patient should receive weight-based dosing of durvalumab **CCI** mg/kg **CCI** and tremelimumab **CCI** mg/kg **CCI**, after consultation between The Investigator and the Study physician, until the weight increases to  $>30$  kg, at which point the patient should receive the original assigned fixed dose of durvalumab **CCI** mg **CCI** with or without tremelimumab **CCI** mg **CCI**.)

Tremelimumab will be administered first; the durvalumab infusion will start immediately after the end of the tremelimumab infusion. The standard infusion time is 1 hour ( $\pm 5$  minutes). Less than 55 minutes is considered a deviation. In the event that there are interruptions during infusion, the total allowed time should not exceed 8 hours at room temperature. If there are

clinically significant concerns after the first cycle, then, at the discretion of the Investigator, all other cycles of durvalumab can be given up to 1 hour after the tremelimumab infusion has finished.

**Figure 3 Durvalumab [REDACTED] mg plus tremelimumab [REDACTED] mg [REDACTED] combination therapy dosing schedule (Arm B)**

[figure not shown]
Durva Durvalumab; D/C Discontinuation; PD Progressive disease; Treme Tremelimumab.

**Durvalumab [REDACTED] mg plus tremelimumab [REDACTED] mg [REDACTED] combination therapy (Arm C)**

Patients in Arm C will receive durvalumab [REDACTED] mg plus tremelimumab [REDACTED] mg [REDACTED] at Week 0, followed by durvalumab [REDACTED] mg monotherapy [REDACTED] starting [REDACTED] after the first and final infusion of the combination therapy until confirmed PD, unacceptable toxicity, or any discontinuation criteria are met (Figure 4). (Note: If a patient's weight decreases to 30kg or below ( $\leq 30$  kg), the patient should receive weight-based dosing of durvalumab [REDACTED] mg/kg [REDACTED] and tremelimumab [REDACTED] mg/kg, after consultation between investigator and study physician, until the weight increases to  $>30$  kg, at which point the patient should receive the original assigned fixed dose of durvalumab [REDACTED] mg Q4W with or without tremelimumab [REDACTED] mg.)

Tremelimumab will be administered first; the durvalumab infusion will start immediately after the end of the tremelimumab infusion. Standard infusion time is 1 hour ( $\pm 5$  minutes). Less than 55 minutes is considered a deviation. In the event that there are interruptions during infusion, the total allowed time should not exceed 8 hours at room temperature. If there are clinically significant concerns after the first cycle, then, at the discretion of the Investigator, all other cycles of durvalumab can be given up to 1 hour after the tremelimumab infusion has finished.

**Figure 4 Durvalumab [REDACTED] mg plus tremelimumab [REDACTED] mg [REDACTED] combination therapy dosing schedule**

Durva Durvalumab; D/C Discontinuation; PD Progressive disease; Treme Tremelimumab.

#### **Sorafenib [REDACTED] mg [REDACTED] (Arm D)**

Patients in the sorafenib arm will receive [REDACTED] mg ([REDACTED] -mg tablets) orally [REDACTED] until PD, unacceptable toxicity, or any discontinuation criteria are met.

Dose reductions for the management of adverse drug reactions will be based on the locally approved product label for sorafenib. In countries where sorafenib is not approved, the following modification will be followed: sorafenib dose may be reduced to [REDACTED] mg ([REDACTED] -mg tablets) orally [REDACTED]. If additional dose reduction is required, the sorafenib dose may be reduced to a single [REDACTED]-mg dose [REDACTED] mg tablets) orally [REDACTED]

#### **7.2.1 Duration of treatment, treatment through disease progression, and rechallenge**

Any time during the treatment period, the patients who meet study discontinuation criteria (Section 3.9) and the patients with rapid tumor progression or symptomatic progression that requires urgent medical intervention (eg, central nervous system metastasis, respiratory failure due to tumor compression, spinal cord compression) will not be eligible for continuing study treatment.

Crossover within the study arms will not be permitted for any of the treatment arms with the exception of rechallenge in Arm B.

##### **7.2.1.1 Treatment through disease progression**

Patients in all treatment arms may continue receiving their originally assigned treatment, at the Investigator's discretion, after the first overall time point assessment of PD by RECIST 1.1 until PD is confirmed on a follow-up scan evaluated by Confirmation of Radiological Progression criteria (Appendix B). A subsequent scan is required following the assessment of PD by RECIST 1.1, preferably at the next scheduled visit and no earlier than 4 weeks after the previous assessment of PD.

Patients in all arms with confirmed PD who, in the Investigator's opinion, continue to receive benefit from their assigned treatment and meet the criteria for treatment in the setting of PD may continue to receive their assigned treatment (Section 7.2.1.3). However, patients who develop progression in TLs after a clear response to therapy as defined by RECIST 1.1 will not be permitted to continue therapy.

#### 7.2.1.2 Rechallenge option for durvalumab and tremelimumab combination therapy arms

Patients in the durvalumab and tremelimumab combination arms (Arm B and Arm C), who complete their first 4 assigned dosing cycles and, in the investigator's opinion, are benefiting from study drug(s), but have evidence of PD with or without confirmation according to RECIST 1.1 during the subsequent durvalumab monotherapy dosing portion, can be rechallenged. Patients must meet eligibility criteria for rechallenge (Section 7.2.1.3), and are only eligible for rechallenge once. Rechallenge cannot begin earlier than **Cycle 6** of their assigned treatment arm.

- **Patients in Arm B** (durvalumab **CCI** mg and tremelimumab **CCI** mg **CCI** arm): Patients will be rechallenged with tremelimumab **CCI** mg **CCI** or tremelimumab **CCI** mg **CCI** and durvalumab **CCI** mg **CCI** (with prior approval from the AstraZeneca Study Physician), followed by **CCI** mg durvalumab monotherapy **CCI** until PD, unacceptable toxicity, or any discontinuation criterion are met.
- **Patients in Arm C** (durvalumab **CCI** mg and tremelimumab **CCI** mg **CCI** arm): Patients will be rechallenged with tremelimumab **CCI** mg and durvalumab **CCI** mg for 1 cycle, followed by durvalumab monotherapy **CCI** mg **CCI** until PD, unacceptable toxicity, or any discontinuation criterion are met.

Patients who meet the criteria for rechallenge for their respective treatment arm are only eligible for rechallenge once and as per their original treatment assignment.

Patients receiving rechallenge with tremelimumab **CCI** mg **CCI** or tremelimumab **CCI** mg **CCI** will follow the same schedule of assessments with the exception of the below assessments, which do not need to be collected a second time:

- PK
- ADA
- **CCI** ) **CCI** )
- **CCI**
- Tumor biopsies
- **CCI**

Rechallenge is permitted only for patients randomized to the durvalumab and tremelimumab combination arms.

#### **7.2.1.3 Criteria for treatment through progression and for rechallenge**

For all patients who are treated through progression or who are rechallenged with tremelimumab in combination with durvalumab, the Investigator should ensure that the following criteria are met:

- Progression should not have occurred after confirmed response (CR or PR as defined by RECIST 1.1) in the TLs (regardless of the appearance of new lesions); ie, the response and progression events both occurred in the TLs during the same treatment period.
- No significant, unacceptable, or irreversible toxicities that indicate continuing treatment will not further benefit the patient.
- There is absence of clinical symptoms or signs indicating clinically significant disease progression accompanied by a decline in World Health Organization (WHO)/ECOG performance status to >1
- There is absence of rapid disease progression or threat to vital organs or critical anatomical sites (eg, central nervous system metastasis, respiratory failure due to tumor compression, or spinal cord compression) requiring urgent alternative medical intervention.
- All eligibility criteria for this study (see Sections 3.1 and 3.2), with the exception of inclusion criteria 5 and 12 and exclusion criterion 23, are met.

Patients who AstraZeneca and the Investigator determine may not continue treatment after PD will be followed up for survival. Patients who have discontinued treatment due to toxicity or symptomatic deterioration, or who have commenced subsequent anticancer therapy, will be followed up until confirmed disease progression and for survival.

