#### **3.1 Inclusion criteria**

For inclusion in the study, patients should fulfill the following criteria:

1. Age  $\geq$ 18 years at the time of screening
2. Body weight  $>$ 30 kg.
3. Written informed consent and any locally required authorization (eg, Health Insurance Portability and Accountability Act in the US, European Union [EU] Data Privacy Directive in the EU) obtained from the patient/legal representative prior to performing any protocol-related procedures, including screening evaluations.
4. Confirmed HCC based on histopathological findings from tumor tissues.
5. Must not have received prior systemic therapy for HCC.
6. Must not be eligible for locoregional therapy for unresectable HCC. For patients who progressed after locoregional therapy for HCC, locoregional therapy must have been completed  $\geq$ 28 days prior to the baseline scan for the current study.
7. Barcelona Clinic Liver Cancer (BCLC) stage B (that is not eligible for locoregional therapy) or stage C. (refer to appendix J)
8. Child-Pugh Score class A. (refer to table 9)
9. ECOG performance status of 0 or 1 at enrollment. (refer to section 5.2.6)
10. Patients with HBV infection, characterized by positive hepatitis B surface antigen (HBsAg) and/or hepatitis B core antibodies (anti-HBcAb) with detectable HBV DNA ( $\geq$ 10 IU/ml or above the limit of detection per local or central lab standard), must be treated with antiviral therapy, as per institutional practice, to ensure adequate viral suppression (HBV DNA  $\leq$ 2000 IU/mL) prior to enrollment. Patients

must remain on antiviral therapy for the study duration and for 6 months after the last dose of study medication. Patients who test positive for anti-hepatitis B core (HBc) with undetectable HBV DNA (<10 IU/ml or under the limit of detection per local or central lab standard) do not require anti-viral therapy prior to enrollment. These subjects will be tested at every cycle to monitor HBV DNA levels and initiate antiviral therapy if HBV DNA is detected ( $\geq 10$  IU/ml or above the limit of detection per local or central lab standard). HBV DNA detectable subjects must initiate and remain on antiviral therapy for the study duration and for 6 months after the last dose of study medication.

11. Patients with HCV infection must have confirmed diagnosis of HCV characterized by the presence of detectable HCV RNA or anti-HCV antibody upon enrollment (management of this disease is per local institutional practice).

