### **3.2 Exclusion criteria**

Patients should not enter the study if any of the following exclusion criteria are fulfilled:

1. Involvement in the planning and/or conduct of the study (applies to both AstraZeneca staff and/or staff at the study site).
2. Previous study drug(s) assignment in the present study.
3. Concurrent enrollment in another clinical study, unless it is an observational (non-interventional) clinical study or during the follow-up period of an interventional study.
4. Have received an investigational product within 28 days prior to the first dose of study drug(s).
5. Any unresolved toxicity National Cancer Institute (NCI) Common Terminology Criteria for Adverse Event (CTCAE) Grade  $\geq 2$  from previous anticancer therapy with the exception of alopecia, vitiligo, and the laboratory values defined in the inclusion criteria:
  - Patients with Grade  $\geq 2$  neuropathy will be evaluated on a case-by-case basis after consultation with the Study Physician.
  - Patients with irreversible toxicity not reasonably expected to be exacerbated by treatment with durvalumab or tremelimumab may be included only after consultation with the Study Physician.
6. Any concurrent chemotherapy, study drug, or biologic or hormonal therapy for cancer treatment. Concurrent use of hormonal therapy for non-cancer-related conditions (eg, hormone replacement therapy) is acceptable.
7. Known allergy or hypersensitivity to any of the study drugs or any of the study drug excipients.
8. Radiotherapy treatment to more than 30% of the bone marrow or with a wide field of radiation within 28 days of the first dose of study drug(s).
9. Major surgical procedure (as defined by the Investigator) within 28 days prior to the first dose of study drug(s). Note: Local surgery of isolated lesions for palliative intent is acceptable.
10. History of allogeneic organ transplantation (eg, liver transplant).
11. History of hepatic encephalopathy within past 12 months or requirement for medications to prevent or control encephalopathy (eg, no lactulose, rifaximin, etc if used for purposes of hepatic encephalopathy).

12. Clinically meaningful ascites, defined as any ascites requiring non-pharmacologic intervention (eg, paracentesis) to maintain symptomatic control, within 6 months prior to the first scheduled dose. Subjects on stable doses of diuretics for ascites for  $\geq 2$  months are eligible.

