  - Malignancy treated with curative intent and with no known active disease  $\geq 5$  years before the first dose of study drug(s) and of low potential risk for recurrence
  - Patients with a history of prostate cancer of stage  $\leq T2cN0M0$  without biochemical recurrence or progression and who in the opinion of the Investigator are not deemed to require active intervention .
  - Adequately treated non-melanoma skin cancer or lentigo maligna without evidence of disease
  - Adequately treated carcinoma in situ without evidence of disease
21. History of leptomeningeal carcinomatosis.
22. History of, or current, brain metastases or spinal cord compression. Patients with suspected brain metastases at screening should have an MRI (preferred) or CT, each preferably with IV contrast of the brain prior to study entry.
23. Known fibrolamellar HCC, sarcomatoid HCC, or mixed cholangiocarcinoma and HCC.
24. History of active primary immunodeficiency.
25. Active infection including tuberculosis (TB) (clinical evaluation that includes clinical history, physical examination and radiographic findings, and TB testing in line with local practice), or human immunodeficiency virus (positive human immunodeficiency virus [HIV] 1/2 antibodies).
26. Current or prior use of immunosuppressive medication within 14 days before the first dose of study drug(s). The following are exceptions to this criterion:
  - Intranasal, inhaled, topical steroids, or local steroid injections (eg, intra-articular injection)
  - Systemic corticosteroids at physiologic doses not to exceed 10 mg/day of prednisone or its equivalent

- Steroids as premedication for hypersensitivity reactions (eg, CT scan premedication)

27. Receipt of live attenuated vaccine within 30 days prior to the first dose of study drug(s). Note: Patients, if enrolled, should not receive live vaccine while receiving study drug(s) and up to 30 days after the last dose of study drug(s).

28. Female patients who are pregnant or breastfeeding, or male or female patients of reproductive potential who are not willing to employ effective birth control from screening to 90 days after the last dose of durvalumab monotherapy or 180 days after the last dose of durvalumab plus tremelimumab combination therapy. Not engaging in sexual activity, as per the patient's preferred and usual lifestyle, for the total duration of the treatment and washout periods is an acceptable practice.

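### Section 7.2.1.3 waives the wrong exclusion criterion for treatment after progression, and the cycle limits on tremelimumab rechallenge appear only in Section 7.2.1.2

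*Protocol*

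**What the plan says.** **Waiver list.** Section 7.2.1.3 covers two groups: patients in any arm treated through progression, and patients rechallenged with tremelimumab plus durvalumab. Its last criterion brings in all of Sections 3.1 and 3.2, "with the exception of inclusion criteria 5 and 12 and exclusion criterion 23, are met". In the current numbering:

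- Inclusion 5 (waived): "Must not have received prior systemic therapy for HCC".
- Inclusion 12 (waived): at least one measurable lesion.
- Exclusion 23 (waived): "Known fibrolamellar HCC, sarcomatoid HCC, or mixed cholangiocarcinoma and HCC".
- Exclusion 2 (not waived): "Previous study drug(s) assignment in the present study".

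Section 7.2.1.1 states that "Patients in all treatment arms may continue receiving their originally assigned treatment" after a first RECIST 1.1 progression, and points to Section 7.2.1.3 for treatment beyond confirmed progression. Section 7.2.1.2 points to Section 7.2.1.3 for rechallenge eligibility.

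**Rechallenge timing.** Section 7.2.1.2 applies to patients in the combination arms ("Arm B and Arm C), who complete their first 4 assigned dosing cycles") who then progress "during the subsequent durvalumab monotherapy dosing portion, can be rechallenged". It adds that rechallenge may not start before Cycle 6. The synopsis, Section 1.4 and Section 5.1 ask for completion of the assigned combination dosing, benefit in the investigator's opinion and later progression on durvalumab monotherapy. They then refer to Section 7.2.1.3. Table 2 footnote q is to the same effect. None of these four places states a number of cycles or an earliest cycle.

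**The concern.** Both parts are operative rules about who may receive further study drug after progression, and when.

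The authors of Section 7.2.1.3 evidently saw that entry criteria cannot all hold for a treated patient, because they waived inclusion 5. The exclusion they paired with it does not serve that purpose. Treatment does not change histology, whereas assignment to study drug in this trial is the one thing that all these patients share.

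The timing limits matter most in Arm C, where combination dosing ends with the first infusion. A site working from the synopsis, Section 1.4 or Section 5.1 is sent to Section 7.2.1.3, which has no cycle condition. Section 1.4 and footnote q do cite Section 7.2.1.2, but only in connection with Arm B. The Study Physician approval written into the rechallenge text also concerns Arm B; the Arm C instruction in Section 7.2.1.2 states no such step.

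At stake are the consistency and safety of a second tremelimumab exposure and the make-up of the rechallenged set. Section 8.4.1.3 names a PFS-from-rechallenge variable for that set (its definition is redacted), and Section 8.5.7 allows separate safety summaries of rechallenge.

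**Working it through.** The plan gives no figure to reproduce here. The check is a comparison of sections plus a cycle calendar.

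**1. Waiver list against the criteria**

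| Criterion | Status in 7.2.1.3 | Position of a randomized, treated patient |
|---|---|---|
| Inclusion 5, no earlier systemic therapy | waived | Study treatment breaks it; the waiver is needed |
| Inclusion 12, measurable lesion | waived | May no longer hold on treatment; the waiver makes sense |
| Exclusion 23, histology | waived | Not changed by treatment; no visible purpose |
| Exclusion 2, prior assignment in this trial | not waived | Met by every randomized patient |

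The criterion requires every exclusion outside the waiver list to be absent. Exclusion 2 is outside the list and is present in every randomized patient. So the number of patients who literally satisfy the criterion is zero, although Sections 7.2.1.1 and 7.2.1.2 set out to allow continuation and rechallenge.

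**2. Cycle calendar for Arm C**

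Inputs: visits every 4 weeks (Table 2, footnote a); scans every 8 weeks for the first 48 weeks (synopsis, Tumor assessments); one combination infusion, at Week 0 (Section 7.2, Arm C). Dose delays and the scan window of ±1 week are set aside.

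- Day 1 of cycle k falls at week 4 × (k − 1).
- Cycle 4 is complete when Cycle 5 begins: 4 × (5 − 1) = Week 16.
- Cycle 6 Day 1: 4 × (6 − 1) = Week 20.
- Scheduled scans before Week 20: Weeks 8 and 16.

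For progression found once four cycles are complete, the earliest start under Section 7.2.1.2 is the later of the scan week and Week 20. Under the shorter statements it is the scan week, provided their other conditions hold.

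| Progression at scan | Shorter statements | Section 7.2.1.2 | Difference |
|---|---|---|---|
| Week 16 | Week 16 (Cycle 5) | Week 20 (Cycle 6) | 20 − 16 = 4 weeks, one cycle |
| Week 24 | Week 24 | Week 24 | 0 |

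The gap therefore exists only for progression found before Cycle 6. How many patients that involves cannot be derived from the protocol.

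**The case against.** The best defence of the waiver list is that Section 3.2 governs entry to the study, and that Sections 7.2.1.1 and 7.2.1.2 expressly allow what exclusion 2 would forbid, so no site would read it as a bar. As a prediction of conduct that is probably right, and it limits the harm. It does not rescue the text: Section 7.2.1.3 itself applies Section 3.2 to the post-progression decision and lists the exceptions. It is also fair that the document does not say which criterion was meant if 23 is a slip, and that the exclusion 23 waiver has almost no practical effect, since patients with known excluded histology may not be randomized.

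On timing, the defence is that the four places are summaries of a dedicated and stricter section that sits immediately before Section 7.2.1.3. That stands in part. Sponsor involvement after progression (Section 7.2.1.3 and Appendix B) also limits divergence, although the Appendix B consultation concerns confirmed progression and rechallenge needs no confirmation.

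Several stronger readings are tempting but not supported:

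- *Exclusion 6 needs a waiver too.* It reads "Any concurrent chemotherapy, study drug, or biologic or hormonal therapy for cancer treatment", which literally names study drug. Its natural sense is other anticancer therapy, and Table 10 states the matching on-treatment rule with the trial's own drugs excepted.
- *The shorter statements contradict Section 7.2.1.2.* They omit its limits; following Section 7.2.1.2 satisfies all of them.
- *It is unclear whether Arm C monotherapy cycles count.* They must, because Section 7.2.1.2 applies the four-cycle rule to Arm C, which has only one combination infusion.
- *Rechallenge at Week 8, 20 − 8 = 12 weeks early.* The same sentences require benefit followed by progression, which progression at the first scan will rarely fit. Under Section 7.2.1.2 that early progression does not qualify on its own in any case.

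**Conclusion.** Wrong as written, and minor. Two points hold:

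- The waiver list in Section 7.2.1.3 excuses a criterion irrelevant to re-treatment and leaves in force one that every randomized patient literally meets.
- The limits on rechallenge stand only in Section 7.2.1.2. A reader of the synopsis, Sections 1.4 and 5.1 or footnote q could rechallenge an Arm C patient too early, by one 4-week cycle for progression at the Week 16 scan and by nothing from Week 24 on.

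The timing result assumes 4-week cycles without delay and a Week 16 scan that falls once Cycle 4 is complete. The waiver result rests on the literal wording of exclusion 2; most sites would probably work around it.

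A reader might infer that the primary comparison is compromised because Arm C is the arm chiefly affected. The documents do not support that. OS is compared by randomized arm regardless of treatment received, so intention-to-treat OS, alpha and power are untouched. The timing gap also matters less now: this version is dated June 2024, while the final primary analysis was expected in Q4 2021, so few early decisions are likely to remain in the global cohort. Section 7.2.1.3 still applies to patients who stay on assigned treatment.

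**What to change.** 1. In Section 7.2.1.3, add exclusion 2 to the waived criteria. Remove the exclusion 23 waiver unless the sponsor confirms that it was intended. Leave exclusion 6 as it is.
2. In the synopsis, Section 1.4, Section 5.1 and Table 2 footnote q, state that rechallenge in both combination arms is subject to Section 7.2.1.2, including completion of four cycles and no start before Cycle 6.

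The cost is a few words of protocol text and a clarification letter to sites. No data collection or analysis changes.
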